3 STATISTICAL ANALYSES

3.1 GENERAL CONSIDERATIONS

In general, continuous data will be summarized using the number of observations available, mean, standard deviation (SD), median, interquartile range (Q1, Q3), minimum, and maximum.

Categorical and ordinal data will be summarized using the count and percentage of participants.

No pre-specified success criterion or formal statistical hypothesis testing is planned. No statistical adjustment on interim analyses is planned.

When the notion of IMP is mentioned in the SAP, this refers to the study IMP.

The baseline value is defined as the last available value before the first dose of IMP, including participants who have received a dose of marketed caplacizumab for the presenting episode of iTP within 4 hours prior to enrollment. For participants enrolled but not treated with IMP, the baseline value is defined as the last available value before enrollment.

Efficacy endpoints derived from laboratory data (platelet count, lactate dehydrogenase [LDH], cardiac troponin I [cTnI], creatinine, ADAMTS13 activity) will be analyzed using central measurements, unless they are missing for a visit but the local value available, in which case the local value will be used under certain conditions (see [Section 5.4](#)). A central measurement will be considered missing if the recorded status is “NOT DONE” and there is a reason for this status or if status is “NOT PERFORMED”.

The observation period will be divided into 4 segments:

- The **pre-treatment period** is defined as the period up to the first caplacizumab administration (whatever marketed or study IMP).
- The **treatment-emergent (TE) period** is defined as the period from the first caplacizumab administration (whatever marketed or study IMP) up to the last caplacizumab administration **+ 28 days**. The TE period includes the following 2 periods:
 - The **on-treatment period** is defined as the period from the caplacizumab administration (whatever marketed or study IMP) to the last administration of caplacizumab.
 - The **residual treatment period** is defined as the period from the end of the on-treatment period to the end of the TE period.
- The **post TE period** is defined as the period from the end of the TE period.

The **overall study period** is defined as the time from the first caplacizumab administration (whatever marketed or study IMP) until the end of the study.

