Platelet count ^j	x ^g	x	x ^g	x	(x) ⁱ	x ^g	x	x	x ^g	x
Blood smear ^k	x ^g									
LDH ^l	x ^g	x	x ^g	x	(x) ⁱ	x ^g	x	x	x ^g	x
m	g					g			g	x

^a;GCS = Glasgow Coma Scale; IMP = investigational medicinal product; IV = intravenous; LDH = lactate dehydrogenase; PD = pharmacodynamics; PK = pharmacokinetics; RICO = ristocetin cofactor activity; SC = subcutaneous; TPE = therapeutic plasma exchange; TTP = thrombotic thrombocytopenic purpura; vWF = von Willebrand Factor.

^a Time (hour/minute) is expressed in reference to the first administration of IMP (T0H). In cases in which the participant has received and tolerated a dose of marketed caplacizumab for the presenting episode of iTPP within 4 hours prior to ICF signing, see footnote ^c below for interpretation of the time.

^b If TPE starts, blood draws during the TPE should be done only if possible.

- c If a participant has received and tolerated a dose of marketed caplacizumab IV for the presenting episode of iTTP within 4 hours prior to enrollment, the specific time of this dose should be documented, the IV dose of study intervention at 0H will be skipped and the subcutaneous dose of caplacizumab due at 4-6H after the pre-study dose, will be the first dose of study intervention. In these cases, all subsequent administrations of study intervention will continue to follow this schedule. The laboratory sampling schedule should remain unchanged (the time [hour/minute] for lab sampling is then expressed in reference to the time of enrollment).
- d First dose of the study intervention is to be administered IV. A second dose is to be administered SC 4 to 6 hours after the IV dose on Day 1 followed by daily SC dose administration. A time window of \pm 1 hour is allowed for the daily SC study intervention administrations. An exception to this is detailed in footnote [a](#).
- e For participants for whom TPE needs to be started only: TPE with plasma (eg, fresh frozen plasma, solvent detergent/viral-inactivated plasma, cryosupernatant) at 1 to $1.5 \times$ estimated plasma volume daily as of enrollment. See details in [Section 4.1](#).
- f Clinical laboratory analyses included hematology, coagulation parameters and clinical chemistry ([Section 10.2](#)).
- g Pre-cplacizumab dose.
- h Sample should be drawn before IMP administration and as close as possible to the IMP administration.
- i Optional assessments.

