- If the baseline central laboratory ADAMTS13 activity is >20% of normal → **Caplacizumab therapy should be discontinued**, and other diagnoses should be considered. Please see [Section 7](#) of the protocol for additional details.

2. Immunosuppressive therapy:

- Corticosteroid therapy: It is expected that all participants will receive corticosteroids. Recommended dose: Prednisone or Prednisolone 1.0-1.5 mg/kg/day, IV or oral, for 1 week and taper over 3 to 4 weeks based on institutional guidelines. The dose and duration of therapy may be adjusted as clinically indicated.

- Anti-CD20 antibody therapy (rituximab or biosimilar): Recommend starting anti-CD20 antibody therapy at the beginning of the study, once iTTP diagnosis is confirmed (ADAMTS13 activity level <10%) and is required if ADAMTS13 activity level remains <10%, 1 week after platelet count normalization or stop of TPE (if TPE was started)

Recommended dose:

375 mg/m² IV infusion (as per instructions on package insert) × 3-4 doses once a week or as per institutional guidelines.

Note:

If there is inadequate response to the initial IST regimen (corticosteroids with or without anti-CD20 antibody therapy) and ADAMTS13 activity level remains <10% after 4 weeks of therapy, the Investigator may consider optimizing IST further (including adding anti-CD20 antibody if not done before) or consider alternative immunosuppressive therapies as per local standard of care.

Therapeutic Plasma Exchange (TPE):

After the first 24 hours of treatment (cplacizumab + IST) (or during the first 24 hours per the judgement of the investigator if there is any evidence of clinical deterioration, as explained below), TPE may be started under the conditions listed below. Initial response to therapy will be evaluated based on laboratory data obtained during the first 24-hours including those performed at the 24-hour timepoint. However, please note that the platelet response is expected within the first 6 to 12 hours based on previously published data (2).

Cplacizumab and IST will be continued after starting TPE.

TPE may be started:

- If there is no initial response to therapy defined as absence of increase from baseline in platelet counts (over at least 2 consecutive values) and absence of decrease from baseline in LDH (at least 2 consecutive values) after 24 hours of treatment.

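### For participants pre-dosed with marketed caplacizumab, the SAP's baseline falls inside its own treatment period, and Protocol 1.3.4 labels some post-dose samples as pre-dose

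*SAP*

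**What the plan says.** **Baseline.** SAP Section 3.1 defines baseline as the "last available value before the first dose of IMP, including participants who have received a dose of marketed caplacizumab" for the presenting episode. It adds: "When the notion of IMP is mentioned in the SAP, this refers to the study IMP". The marketed dose therefore does not count as the first dose for baseline.

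**Periods.** The same section defines the treatment-emergent period as the "period from the first caplacizumab administration (whatever marketed or study IMP) up to the last caplacizumab administration" plus 28 days. The on-treatment and overall study periods also begin at the first caplacizumab of either kind.

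**Dosing and sampling.** Exclusion criterion E 13 limits the gap between marketed dose and enrollment to 4 hours. Under Protocol Section 1.3.4, footnote c, the 0H IV dose is skipped for these participants and "the subcutaneous dose of caplacizumab due at 4-6H after the pre-study dose, will be the first dose of study intervention". The sampling schedule is unchanged, but "the time [hour/minute] for lab sampling is then expressed in reference to the time of enrollment". Footnote g marks the 0H, 4-6H, 24H and 48H platelet and LDH samples "Pre-cplacizumab dose" (spelling as in the document).

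**Who is included.** SAP Section 2 keeps these participants in every analysis population. SAP Section 3.6.1.1 will report how many there were; no expected number is given.

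**The concern.** In Protocol Section 9.2.1, baseline and the observation periods both hang on the first IMP dose. The SAP moved the periods to the first caplacizumab of either kind and left baseline on the first study dose. In pre-dosed participants the reference value therefore no longer precedes treatment.

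Three things read that value: the change-from-baseline tables for laboratory variables and vital signs (SAP 3.6.3.1), the baseline status categories for potentially clinically significant abnormalities (PCSA) and ECG (same section), and the baseline disease characteristics (SAP 5.3). Any movement in the first hours after the IV dose is absorbed into baseline, and pre-dosed participants are pooled with others whose baseline is drug-free.

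The second problem is that doses and samples run on different clocks while the pre-dose labels stay fixed. Some samples so labelled must then be drawn after a dose.

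**Working it through.** The plan states no figure on this point, so there is none to reproduce. The check is a comparison of rules and clock arithmetic.

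**Step 1: where baseline falls.** Put enrollment at 0 h and the marketed IV dose at −d h, with 0 ≤ d ≤ 4 (E 13). The first study dose is the SC dose, due 4 to 6 h after the marketed dose, so at 4 − d to 6 − d h. The treatment period starts at −d. Any value taken after −d and before the SC dose is on-treatment, yet qualifies as baseline.

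- *Central laboratory.* Protocol 1.3.4 (footnotes j and l) sends the baseline, 24-, 48- and 60-hour and later daily platelet and LDH samples to the central laboratory. The last scheduled central value before the SC dose is the 0H sample, d h after the marketed dose: at most about 4 h.
- *Local laboratory.* The 3H sample is local only. It must precede the SC dose when 4 − d > 3 (d < 1) and may do so when 6 − d > 3 (d < 3). At d = 0.5 the SC dose is due at 3.5 to 5.5 h, so the 3H value, 3.5 h after drug, replaces the 0H value as local baseline. No baseline can be later than 6 h after the marketed dose if the SC dose is on time.

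**Step 2: the pre-dose labels.** Sample windows are 4 to 6 h, 24 ± 2 h and 48 ± 3 h from enrollment (Protocol 1.3.4). Daily SC doses have a ± 1 h window (footnote d). Assume that later doses keep the pre-study clock. The Day 2 dose is then at 24 − d ± 1 h and the Day 3 dose at 48 − d ± 1 h. Sample time minus dose time ranges as follows:

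- 4-6H sample: 4 − (6 − d) = d − 2, to 6 − (4 − d) = d + 2
- 24H sample: 22 − (25 − d) = d − 3, to 26 − (23 − d) = d + 3
- 48H sample: 45 − (49 − d) = d − 4, to 51 − (47 − d) = d + 4

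| d (h) | SC dose due (h) | 4-6H minus SC dose (h) | 24H minus Day 2 dose (h) | 48H minus Day 3 dose (h) |
|---|---|---|---|---|
| 0.5 | 3.5 to 5.5 | −1.5 to 2.5 | −2.5 to 3.5 | −3.5 to 4.5 |
| 1 | 3 to 5 | −1 to 3 | −2 to 4 | −3 to 5 |
| 2 | 2 to 4 | 0 to 4 | −1 to 5 | −2 to 6 |
| 3 | 1 to 3 | 1 to 5 | 0 to 6 | −1 to 7 |
| 4 | 0 to 2 | 2 to 6 | 1 to 7 | 0 to 8 |

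A negative lower limit means that the sample can still precede the dose. The 0H sample always follows caplacizumab. The 4-6H sample must follow the SC dose when d > 2, and the 24H sample must follow the Day 2 dose when d > 3. The 48H sample is never forced after the Day 3 dose within d ≤ 4, although at d = 4 it can only coincide with it at the edge of both windows.

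**Step 3: what does not read this baseline.** Remission rests on absolute platelet and LDH thresholds (SAP 3.2.1, 5.4). The modified ITT (mITT) population depends on baseline ADAMTS13 activity, which the documents do not describe as altered by caplacizumab. Time to platelet response starts at first caplacizumab of either kind (SAP 5.4).

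**The case against.** **The study-IMP baseline is deliberate and matches other SAP rules.** The PCSA and ECG windows (3.6.3.1), Day 1 in Table 7 and the definition of prior medication all start at the first study IMP. Protocol Section 8 acknowledges an exception for baseline samples in this group. This stands as a caution about the repair: moving baseline alone would leave values between the two doses in neither the baseline nor the PCSA window. It does not remove the conflict with the period definitions, and no reason is given for it.

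**Sites must assess before dosing** (Protocol 1.3.2 footnote a; Section 8). That preserves the 4-6H label only by breaking a clock: when d > 2, either the SC dose is given later than footnote c states or the sample is drawn early. For Day 2 and Day 3 the objection carries more weight. Footnote o of Section 1.3.2 sends later doses to the Section 1.3.4 schedule, which can be read as the chart's own 24H and 48H slots. On that reading the later shift disappears. A reader might infer that all Day 2 and Day 3 samples are post-dose; the documents do not support that.

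**A reader might infer that the 3H value displaces the main baseline.** It cannot displace a central value. Efficacy endpoints use central data unless missing, and the safety tables show local and central data separately.

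**A reader might infer a biased primary endpoint**, because one condition for starting plasma exchange compares 24-hour platelets and LDH with baseline. That condition is permissive, needs both markers to fail and is judged at the bedside, so SAP 3.1 does not govern it. The protocol also states that "platelet response is expected within the first 6 to 12 hours based on previously published data", and a 0H value at most about 4 h after drug precedes that range.

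**A reader might infer that pharmacokinetic and pharmacodynamic summaries mix peak and trough values.** The relevant analysis text is not shown, actual pharmacokinetic sample times are recorded (Protocol 8.4), and the PK population requires documented dosing and sampling times.

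**Conclusion.** The point holds for pre-dosed participants only. Their baseline lies inside the SAP's own treatment period, by up to about 4 h for central platelets and LDH and up to 6 h for local values. The pre-dose label is always wrong at 0H and necessarily wrong at 4-6H when the gap exceeds 2 h. It is necessarily wrong at 24H only when the gap exceeds 3 h and later doses keep the pre-study clock.

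The consequences are confined to baseline description, change from baseline and baseline status for PCSA and ECG. The direct effect on the primary responder rate is small, and no figure in the documents shows how far values move in the first 4 h. How much the tables shift depends on the number of pre-dosed participants, which is not given; the rationale for protocol amendment 01 says that early IV dosing is standard in many sites. It is worth correcting before the database is locked, but it does not threaten the main result.

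**What to change.** **SAP 3.1.** For platelets, LDH, troponin, creatinine and other safety variables, define baseline as the last value before the first caplacizumab administration, marketed or study. Use the local values from before consent that Protocol 1.3.1 already accepts (platelets, creatinine and troponin within 24 h, ECG within 4 h) where they pre-date that dose; for troponin, only where the assay is the same. Otherwise use the 0H sample, never a later one, and flag it as post-drug. Keep the ADAMTS13 baseline, and so mITT membership, exactly as now defined.

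**SAP 3.6.3.1.** Start the PCSA and ECG windows at the first caplacizumab dose so that they match the treatment-emergent period. A flagged 0H value serving as baseline should not also count as post-baseline.

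**Protocol 1.3.4.** Footnotes a, c and g, and footnote o of Section 1.3.2, must be reconciled. They disagree on the clock, and footnote a counts back from consent where footnote c counts back from enrollment. Which schedule applies is for the sponsor to settle. In analysis, do not label or summarise as pre-dose any sample whose recorded time follows a dose.

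**Cost.** A short SAP revision, a programming flag and footnote edits. Some pre-dosed participants will have a local rather than central baseline. LDH is not among the listed screening tests, so it will often fall back to the flagged 0H value.

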Recently, real-world evidence data was published from a prospective study in France in which 90 patients treated with a triplet regimen (TPE, IST with corticosteroids and rituximab, and caplacizumab) were compared to a historical cohort of 180 iTTP patients managed with the standard regimen (TPE and corticosteroids, with rituximab as salvage therapy) (24). The primary outcome was a composite of refractoriness and death within 30 days since diagnosis. The composite primary outcome was met for 12.2% of historical patients versus only 2.2% of patients in the triplet regimen met the composite primary outcome of refractoriness and death within 30 days since diagnosis ($p=0.01\%$). The study also confirmed the effect of caplacizumab on the prevention of exacerbation: a significant decrease in exacerbations was noted in the triplet regimen cohort compared to the historical cohort (3.4% vs. 44%, $p<0.01$). Patients in the triplet cohort showed durable platelet recovery 1.8 times faster than historical patients (95% confidence interval [CI], 1.41-2.36, $p<0.01$), and required fewer TPE sessions (5 days vs. 10 days, $p<0.01$). After a median follow-up of 127 days (range: 47-200 days), only one clinical relapse (1.1%) occurred in the triplet regimen cohort (patient with ADAMTS13 <10% at time of stopping caplacizumab) suggesting that it is possible to decrease disease recurrence when caplacizumab is given until the underlying disease is controlled.

In addition to the benefits provided by caplacizumab with immunosuppression and TPE regimen as above, the proposed caplacizumab regimen is expected to provide additional direct benefits to iTTP patients. As the regimen does not include first-line TPE, there will be decreased treatment-related burden with reduction in TPE-related complications including procedural complications (invasive catheter placement and associated AEs such as bleeding, thrombosis, infections, pneumothorax) and plasma related complications such as allergic reactions including anaphylaxis, serum sickness, hypotension requiring dopamine). In addition, this caplacizumab treatment regimen will decrease the health care related financial impact on the patient and improve quality-of-life due to decreased burden of care (relative to caplacizumab with first-line TPE) and increase patient satisfaction with treatment.

This regimen will also result in a reduction in iTTP-associated healthcare resource utilization (HCRU).

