Participants will be followed up for a period of 12 weeks after completion of study treatment. During the follow-up period they will be evaluated in the out-patient setting at 7 ± 1 days, 28 ± 1 days and 12 weeks (± 3 days) after the last dose of the IMP.

There will be two additional follow-up visits (14 ± 1 days and 21 ± 1 days after last caplacizumab dosing) for participants who do not have ADAMTS13 activity levels of $\geq 50\%$ at the time of caplacizumab discontinuation.

A physical exam will be performed, and laboratory tests including platelet count and organ damage markers will be obtained during the visits.

Treatment of a first clinical recurrence (exacerbation or relapse):

Clinical Exacerbation is defined as after a Clinical Response and before a Clinical Remission, platelet count decreases to $<150 \times 10^9/L$ (with other causes of thrombocytopenia excluded), with or without clinical evidence of new or progressive ischemic organ injury, within 30 days of stopping TPE or anti-vWF therapy.

Clinical Relapse is defined as after a Clinical Remission, platelet count decreases to $<150 \times 10^9/L$ (with other causes of thrombocytopenia ruled out), with or without clinical evidence of new ischemic organ injury. A Clinical Relapse must be confirmed by documentation of severe ADAMTS13 deficiency ($<10\%$).

In case of a first clinical recurrence (exacerbation or relapse) of the presenting TTP episode during the overall study period, it is up to the Investigators to adjust the ongoing treatment plan, which may include start or restart of TPE and adjustment of IST regimen and caplacizumab therapy. In case that caplacizumab treatment is maintained for a first clinical recurrence (exacerbation or relapse), the visit schedule will be the same as during the initial treatment period.

If a participant develops a second clinical recurrence (exacerbation or relapse) the participant will discontinue from the study ([Section 7.1.1](#)). At the time of discontinuing from the study, if possible, an early discontinuation visit should be conducted, as shown in the SoA ([Section 1.3](#)). See SoA for data to be collected at the time of study discontinuation and follow-up and for any further evaluations that need to be completed.

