9.2.1 General considerations

In general, continuous data will be summarized using the number of observations available, mean, SD, median, [Q1, Q3], minimum, and maximum, where appropriate. Categorical and ordinal data will be summarized using the count and percentage of participants.

No pre-specified success criterion and formal statistical hypothesis testing is planned.
No statistical adjustment on interim analyses.

The baseline value is defined as the last available value before the first dose of open-label IMP. For participants enrolled but not treated, the baseline value is defined as the last available value before enrollment.

The observation period will be divided into 4 segments:

- The **pre-treatment period** is defined as the period up to first IMP administration.
- The **treatment-emergent (TE) period** is defined as the period from the first IMP administration to the last IMP administration + 28 days. The treatment-emergent period includes the following 2 periods:
 - The **on-treatment period** is defined as the period from the first IMP administration to the last administration of the IMP,
 - The **residual treatment period** is defined as the period from the end of the on-treatment period to the end of the treatment-emergent period.
- The **post treatment-emergent (TE) period** is defined as the period from the end of the treatment emergent period.

The **overall study period** for analysis is defined as the time from first IMP administration until the end of the study.

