1 INTRODUCTION

1.1 STUDY DESIGN

This is an open-label, single-arm, Phase 3, multicenter study to evaluate the efficacy and safety of caplacizumab and immunosuppressive therapy (IST) without first-line therapeutic plasma exchange (TPE) in adults with immune-mediated thrombotic thrombocytopenic purpura (iTTP).

The anticipated study duration per participant, without a recurrence while on therapy, is a maximum of approximately 24 weeks (ie, approximately 1 day for screening + maximum 12 weeks of treatment for the presenting episode + 12 weeks of follow-up). All participants will receive open-label caplacizumab daily until sustained disintegrin and metalloproteinase with a thrombospondin type 1 motif13 (ADAMTS13) activity normalization ($\geq 50\%$) is achieved at 2 consecutive visits, after platelet count normalization (defined as $\geq 150 \times 10^9/L$ for 2 consecutive values) or 12 weeks of caplacizumab treatment, whichever occurs first.

For participants who experienced a first clinical recurrence (exacerbation or relapse) during the overall study period, the ongoing treatment plan may be adjusted including a start or re-start of TPE and adjustment of IST regimen and caplacizumab therapy. In case that caplacizumab treatment is maintained for a first clinical recurrence, the visit schedule will be the same as during the initial treatment period.

[figure not shown]
The primary analysis will be conducted after study completion of all participants, ie, when all the participants will have discontinued from the study.

In addition, an interim analysis (IA) will be conducted after the first 30 participants with baseline ADAMTS13 activity of $<10\%$ have completed the study (eg ended treatment period per protocol and completed the follow-up period of 12 weeks) (see [Section 3.8](#) for further details). A Data Monitoring Committee (DMC), independent from the Sponsor, will be appointed to monitor the safety and the scientific integrity of this study on an on-going basis, and to provide in a timely fashion appropriate recommendations to the Sponsor.

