3.6.1 Extent of exposure and compliance

The extent of study IMP exposure will be assessed by the duration of IMP exposure, and the overall exposure for caplacizumab treatment will be presented as described below. All information will be summarized within the safety population.

Duration of IMP exposure

Duration of IMP exposure (in days) is defined by date of the last administration of caplacizumab – date of first administration of caplacizumab (whether marketed or study caplacizumab) + 1 day, regardless of unplanned intermittent discontinuations.

The duration of IMP exposure will be calculated from the maximum date reported among **Treatment Status** form, **IMP administration on Site** form, **Exposure (eDiary)** form, and **Exposure (paper IMP diary)** form.

For DMC review specifically, the duration of IMP exposure will be the minimal duration of IMP exposure.

Duration of IMP exposure will be summarized quantitatively.

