3.6.1.1 Overall exposure

The number of treated participants and actual and cumulative dose for caplacizumab will be presented. Caplacizumab exposure data will be presented on-site and off-site separately.

The dose information administered on-site will be assessed using the following variables:

- intended daily dose (mg)
- actual total daily dose (mg)
- cumulative dose (mg)

- route
- reason in case of partial volume injected
- reason for not taken

The dose information administered off-site will be assessed using e-diary information with the help of the following variables:

- part of abdomen injected
- person in charge of the administration
- reason for the non-administration if any
- if there were partial administration and the reason if any

In addition, the number of participants who started with marketed caplacizumab will be presented, as well as the number of participants who re-initiated the treatment.

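### The on-treatment relapse proportion cannot register an event in a course without a 30-day drug-free gap, and later re-dosing moves an off-drug recurrence into the on-treatment row (small impact)

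*SAP*

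**What the plan says.** SAP 3.1 gives the on-treatment period as "the period from the caplacizumab administration (whatever marketed or study IMP) to the last administration of caplacizumab". Protocol 9.2.1 has the same form: the period "is defined as the period from the first IMP administration to the last administration of the IMP". Neither text says what happens to a drug-free gap or to a second course. SAP 3.6.1 computes exposure duration in the same way, from first to last date, "regardless of unplanned intermittent discontinuations".

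SAP 3.3 lists the proportions with clinical relapse and with clinical exacerbation among the secondary endpoints. Each is reported for the on-treatment period and for the overall study period, with a two-sided 95% CI.

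SAP 5.4 allows a Clinical Relapse only after a Clinical Remission. SAP 3.2.1 defines Clinical Remission as a sustained Clinical Response with at least 30 days of no TPE and no anti-vWF therapy. SAP 5.4 identifies that therapy as caplacizumab. Clinical Exacerbation lies between Clinical Response and Clinical Remission, within 30 days of stopping TPE or anti-vWF therapy.

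For a first recurrence, protocol 4.1 says "it is up to the Investigators to adjust the ongoing treatment plan". SAP 1.1 says "the ongoing treatment plan may be adjusted including a start or re-start of TPE and adjustment of IST regimen and caplacizumab therapy". SAP 3.6.1.1 will also present "the number of participants who re-initiated the treatment".

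**The concern.** Two things follow from these definitions. First, a relapse needs a drug-free window of at least 30 days before it, while the on-treatment period stops at the last dose. In an ordinary course the on-treatment relapse row cannot hold an event, yet it will be printed as a proportion with a confidence interval. A reader could take a zero there as evidence of protection while on drug.

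Second, the end of the period is set by the last dose whenever it is given. Two participants with the same off-drug recurrence are classified differently if one is dosed again and the other is not. When the row is not zero, the treatment decision that followed the event may be what put it there.

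**Working it through.** **Can a relapse fall inside the period?** Let a course run from day 1 to day L with no gap of 30 days or more. Thirty drug-free days are complete at L + 30 at the earliest, so the first possible relapse day is L + 31.

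- L = 28: day 59. L = 56: day 87. L = 84 (the 12-week maximum): day 115.
- Each is later than L, so none is on-treatment.
- SAP 5.4 counts the 30 days from the date of Clinical Response. This does not change the result, because those days must still be free of caplacizumab.
- ADAMTS13 recovery on drug does not open another route. The relapse definition names Clinical Remission, which the SAP defines separately from Complete ADAMTS13 Remission.

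There is one exception. Protocol 7.1.3 treats a temporary discontinuation as more than one missed dose and sets no upper limit. After an interruption of at least 30 days with Clinical Remission, followed by resumed dosing, a relapse on drug is possible.

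**What does later dosing do?** Illustration with assumed dates and a first course on days 1 to 84:

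| Event | No further dosing | Dosed again | By dosing status at onset |
|---|---|---|---|
| Exacerbation, day 94 | not on-treatment | days 95–122: on-treatment | off-drug |
| Relapse, day 134 | not on-treatment | days 135–162: on-treatment | off-drug |

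In the second row, exposure under SAP 3.6.1 is 162 − 1 + 1 = 162 days, against 84 + 28 = 112 dosing days.

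**How large is it?** N = 55 is the planned mITT size (SAP 4). SAP 3.3 names no interval method for secondary proportions, so I assume Wilson, as for the primary endpoint. As a check, 39/55 gives a lower bound of 57.9%, which matches the plan's 58% for an assumed 70%.

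- 0/55 = 0% (95% CI 0 to 6.5%)
- 1/55 = 1.8% (0.3 to 9.6%)
- 2/55 = 3.6% (1.0 to 12.3%)

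Each participant who moves shifts the row by 1/55 = 1.8 points.

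The documents give no recurrence or re-dosing rate for this regimen. The nearest figures are in protocol 2.3.2, from a cohort of 90 treated with TPE as well.

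- Relapse: "only one clinical relapse (1.1%) occurred in the triplet regimen cohort". 1/90 has a Wilson CI of 0.2 to 6.0%. Expected in 55: 55 × 1/90 = 0.6, with range 55 × 0.0020 = 0.1 to 55 × 0.0603 = 3.3. If 1/90 were the true rate, the chance of no relapse would be 54%, of one 33%, and of two or more 12.5%.
- Exacerbation: 3.4%, with no count given. Expected in 55: 55 × 0.034 = 1.9. Assuming 3/88, the Wilson CI is 1.2 to 9.6%, or about 0.6 to 5.3 of 55.

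These expectations are the most that could move. They would move in full only if every event occurred off drug and was followed by re-dosing.

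**The case against.** The strongest case is that little depends on this. Nothing is tested, the primary endpoint does not use the period, and the overall-period proportion stands beside the on-treatment one for each endpoint. The remission precondition is printed with the relapse definition, so a careful reader can see why the row is empty. All of this stands, and it sets the size of the point. It does not make the on-treatment row interpretable.

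Three further objections also stand.

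- **Direction.** Re-dosing adds events to the on-treatment row, which does not flatter the drug. A reader might infer that the rule hides recurrences. It does not, since the overall-period figures contain all of them.
- **Evidence for re-dosing.** A reader might infer that the SAP plans re-initiation after recurrence. The protocol and SAP 1.1 name restarting only for TPE and speak of adjusting caplacizumab. SAP 3.6.1.1 counts re-initiators without linking them to recurrence, and protocol 7.1.4 uses the same idea for resumption after an adverse event. Re-dosing after recurrence is allowed on a natural reading, but no rate is given. The first half of the point needs no re-dosing.
- **Other capture of on-drug worsening.** The refractory endpoint can be met after a platelet response, on-treatment TPE use is a secondary endpoint, and TTP events are recorded by the investigator. The other endpoints are redacted, so a similar platelet summary may already exist.

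A reader might also infer that on-treatment exacerbation is impossible. It is not: caplacizumab continues after TPE stops (protocol 4.1), so an exacerbation within 30 days of stopping TPE can occur on drug. At the planned 18% needing TPE, about 55 × 0.18 = 10 participants could contribute in this way.

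**Conclusion.** The point holds. As defined, on-treatment relapse cannot register an event in a course without a drug-free gap of at least 30 days, and later dosing can change the period to which an earlier off-drug recurrence is assigned. The first statement follows from the definitions alone. The second also requires that caplacizumab is given again after the event.

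The impact is small: 1.8 points per participant in two descriptive secondary rows. The expected ceilings, about 0.6 relapses (0.1 to 3.3) and 1.9 exacerbations (roughly 0.6 to 5.3), rest on carrying rates over from a regimen that included TPE and on an assumed denominator for the 3.4%. The documents do not support reading this as a threat to the primary result or to the overall recurrence estimates.

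**What to change.** Change the SAP only, and record the change as a documented difference from protocol 9.2.1.

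1. For relapse and exacerbation only, classify each event by dosing status at onset, using the last caplacizumab dose before the event, so that later dosing cannot alter its period. Count events in a drug-free gap as off-drug, and prespecify the gap length from dosing dates already collected. The length should be short: with a threshold above 10 days, the day-94 exacerbation in the illustration would count as on drug. The protocol 7.1.3 criterion of more than one missed dose is one candidate. Leave the on-treatment period unchanged for TPE use, Clinical Response, refractoriness, TTP-related death and safety. Redefining it for all efficacy endpoints would, for example, drop a TTP death during retreatment from the on-treatment row.
2. Footnote the on-treatment relapse row as unable to register events in a course without a drug-free gap of at least 30 days. Base recurrence conclusions on the overall-period proportions.
3. Add a supportive count of platelet falls below 150 × 10⁹/L after Clinical Response while on caplacizumab. This count supplies the on-drug information that the relapse row cannot.

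The cost is one derived flag, one footnote, one table row and a documented SAP–protocol difference. No new data are collected, no endpoint is removed and clinical management does not change.
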